12.1 Valve Removal

Study investigators may consider removing valves due to occurrence of an adverse event (see Section 15.0). Valves may be removed according to the Manufacturer's Instructions for Use.

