12.2 Valve Replacement

Study investigators may consider replacing valves for study participants who expectorate a valve(s) or in cases where the valve(s) was removed due to an adverse event (See Section 14.0) which has since been resolved. Up through the 1-year follow-up time point, valves may be replaced up to a maximum of two times. The treating physician will determine the timing of a valve replacement on a per-patient basis. Valves may be replaced according to the Manufacturer's Instructions for Use.

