12.3 Valve Adjustment

It is anticipated that there may be a few cases in which a valve may not have been initially placed to occlude the treated lobe. In any case where clinical evidence exists that a valve was not placed to block the airway leading into the target lobe, adjustment of the valve may be considered by the investigator. Valve adjustment will be considered to be part of the study procedure since clinical effect with the Pulmonx EBV is thought to be associated with placing valves to achieve lobar occlusion.

Valve adjustment may be performed only once for a study participant and should be performed within 75 days of the study procedure. In any case in which it is necessary to re-schedule a valve adjustment due to a study participant's illness (e.g. COPD exacerbation), the valve adjustment may be conducted up to 90 days post-procedure.

The investigator may consider valve adjustment if both of the following are observed:

- 1) The 45-day HRCT scan, as read by the core radiology reading laboratory and measured using FDA cleared software designed to evaluate HRCT changes, shows less than 50% volumetric reduction in the EBV-treated lobe.
- 2) The 45-day HRCT scan, as read by the core radiology reading laboratory, demonstrates signs indicative of incomplete occlusion, including no valve in a segmental airway, anatomic variation resulting in the valve not occluding accessory branches, leakage around the valve, and incorrect placement.

The post-procedure flow and follow-up testing schedule for study participants having valve adjustment is shown in **Appendix 1** and **Appendix 12**. The bronchoscopy procedure for the valve adjustment will be conducted as described in Section 11.

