- B. Endpoint Analyses: Primary and secondary study endpoints will be analyzed utilizing an intent-to-treat (ITT) population defined as all randomized patients analyzed by the groups to which they were randomly assigned (EBV treatment or control). Consenting patients who qualify for the study and are randomized into the study will be included in the ITT population, regardless of the actual treatment received. Consented patients who are found not to meet the study eligibility criteria prior to randomization will not be included in the intent-to-treat group.
- C. Secondary Analyses: Secondary analyses will also be performed on the study primary and secondary endpoints on a Completed Cases (CC) basis and Per-Protocol (PP) basis. The CC population is defined as all randomized and eligible patients who received study-directed treatment and had 1 year of follow-up. The PP population is defined as all randomized patients who meet study eligibility criteria, who were treated as randomly assigned, and had follow-up for the endpoints. Any visits where protocol violations occurred will be reviewed for possible exclusion from impacted analyses.
- D. Safety Analysis Population: Both the ITT analysis population and ‘As Treated’ (AT) analysis population will be used to assess the safety data. For the AT analysis, study participants will be analyzed based on the treatment they actually received.
- E. Secondary Valve Procedures: If applicable, statistical analyses will also be conducted after sorting patients by the actual treatment received, specifically valve removal, valve replacement, and valve adjustment.

IV. Effectiveness Analyses

There is one primary effectiveness variable, four secondary effectiveness variables, and several additional effectiveness variables.

A. Analysis of the Primary Effectiveness Endpoint

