inter-lobar fissures	percent complete	percentage of participants

V. Adjustment for Potential Confounders

The covariates shown in Table 6 may be potentially influential with respect to the effectiveness endpoints. If any of these covariates are found to be out of balance between the groups (at the two-sided 0.10 level), they will be included in a multivariate analysis, along with an indicator of treatment group, to evaluate their potential effect on the study conclusions. A multivariate logistic regression model will be used for primary and secondary endpoints.

Table 6. Covariates

	Baseline	Procedure
Gender	X	
Age	X	
Clinical Site	X	
6MWD	X	
Patient-reported health status measures (e.g. SGRQ)	X	
Body Mass Index	X	
BODE Index	X	
Medication Use	X	
Residual Volume (RV)	X	
RV % Predicted	X	
Total Lung Capacity (TLC)	X	
TLC % Predicted	X	
RV/TLC	X	
IC/TLC	X	
Vital Capacity	X	
Forced Vital Capacity (FVC)	X	
FVC % Predicted	X	
FEV ₁	X	
FEV ₁ % Predicted	X	
FEV ₁ / FVC	X	
Lobar Volume	Х	
Lobar Destruction Scores	Х	
Ipsilateral DS Heterogeneity	X	
Severity of emphysema (GOLD classification)	X	
Comorbidities	X	
Target Treatment Lobe		Х
Treatment Group		Х

VI. Secondary Valve Procedures

Secondary valve procedures will be evaluated by examining the proportion of patients who undergo valve removal, valve replacement, or valve adjustment, and describing the reasons they occurred. Data for these study participants will be contrasted to data for study participants who did not receive a secondary valve procedure.

VII. Safety Analyses

Evaluation of the short- and long-term adverse events profile during the treatment period, defined as the day of the study procedure until 45 days after the study procedure (short), and in the post-treatment period, defined as 46 days after the study procedure until the 1-year follow-up visit (long). For the Control arm, the date of study procedure will be considered the date of the bronchoscopy assessment. Safety analyses will be performed by examining the percentage of patients that experiences adverse events. The rates and 95% exact confidence intervals will be presented on an event and on a per-patient basis. The percentage of subjects reporting adverse events occurring in at least 3% of subjects in either treatment arm will be compared using a Fisher's Exact test.

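### Contrasting participants with and without a secondary valve procedure is confounded by indication and can make a helpful valve adjustment look harmful

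*Protocol*

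**What the plan says.** Revised SAP section III.E, which supersedes Protocol Appendix 19 but keeps its sentence, provides that where applicable "statistical analyses will also be conducted after sorting patients by the actual treatment received, specifically valve removal, valve replacement, and valve adjustment". Section VI of the revised SAP asks for the proportion with each procedure and the reasons, and then adds: "Data for these study participants will be contrasted to data for study participants who did not receive a secondary valve procedure". It names no test, model, estimand or landmark, does not restrict the comparator, and does not call the result descriptive.

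The protocol sets out who gets each procedure:

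- **Adjustment (12.3).** "The investigator may consider valve adjustment if both of the following are observed": first, that the 45-day HRCT "shows less than 50% volumetric reduction in the EBV-treated lobe"; second, that it "demonstrates signs indicative of incomplete occlusion". On timing: "Valve adjustment may be performed only once for a study participant and should be performed within 75 days of the study procedure". The limit extends to 90 days if illness forces rescheduling.
- **Removal (12.1, 15.4).** "Study investigators may consider removing valves due to occurrence of an adverse event". Section 15.4.8 also allows removal at the participant's request for any reason.
- **Replacement (12.2).** This follows expectoration, which section 15.1 lists among adverse events, or removal for an adverse event that has since resolved.

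The covariate rule in SAP section V responds to imbalance between the groups and uses a treatment-group indicator. Revised Table 6 no longer lists target lobe volume reduction or lobar occlusion.

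**The concern.** Adjustment is offered only after a poor early radiological result, so the adjusted group starts with a worse outlook. The comparator, everyone without a secondary procedure, contains all the good early responders. A crude difference between the two mixes the effect of adjustment with the reason it was offered. For removal and replacement the problem is different but no smaller: the group is usually formed by a harm or a lost valve, so contrasting adverse events with the rest is close to circular.

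Protocol 12.3 treats adjustment as part of the study procedure, and the trial supports a premarket application. A table in which adjusted participants do worse could be read as evidence that adjustment fails, even if it helps. Nothing elsewhere in the SAP guards against that reading. The section V rule is not aimed at this contrast, and the two variables that decide who is eligible for adjustment are not in its covariate list.

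**Working it through.** **The plan's own figures.** The documents give no figure for this contrast. The nearest anchors are in Protocol 20.3.1: 35% EBV and 10% control responders, 2:1, two-sided 0.05, 90% power. The two-proportion formula gives 44 + 88 = 132 without continuity correction and 49 + 98 = 147 with it, matching the stated 147. Allowing for 20% loss, 147/0.80 = 183.75, against 183 stated. The sample size is not in dispute.

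**Illustration A: EBV arm at 35% overall.**

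Inputs:
- EBV arm of 122 (two thirds of the planned 183).
- f, the share adjusted (assumed). The base value of 14.5% is borrowed from the valve-removal rate in the earlier US trial (Protocol 15.4), so it is not an adjustment rate.
- p0, the response rate the adjusted would have had without adjustment (assumed).
- b, the true benefit (assumed).

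The rate in the non-adjusted is (0.35 − f(p0 + b))/(1 − f). The planned contrast is (p0 + b) minus that rate, which simplifies to (p0 + b − 0.35)/(1 − f).

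Base case, f = 0.145, p0 = 0.10, b = 0.10: the others respond at (0.35 − 0.029)/0.855 = 37.5%, and the contrast is 20.0 − 37.5 = −17.5 points. With 18 adjusted and 104 not, the SE is √(0.20×0.80/18 + 0.375×0.625/104) = 10.6 points. In 100,000 binomial draws the contrast was negative in about 95%.

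Contrast in points when the true benefit is +10:

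| p0 | f = 5% | f = 14.5% | f = 25% |
|---|---|---|---|
| 10% | −15.8 | −17.5 | −20.0 |
| 20% | −5.3 | −5.8 | −6.7 |
| 30% (weak selection) | +5.3 | +5.8 | +6.7 |
| 35% (no selection) | +10.5 | +11.7 | +13.3 |

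The expected sign depends only on whether p0 + b reaches 35%, not on f. At p0 = 10% the benefit must exceed 25 points before the expected contrast turns positive.

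**Illustration B: mixture by 45-day volume reduction.**

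Inputs:
- 127 EBV participants (two thirds of the 190 enrolled, revised SAP).
- 20 adjusted, all with reduction under 50% (assumed).
- A share s of the arm under 50% reduction, responding at r0; the rest at r1 (all assumed, chosen to average 35%).

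Non-adjusted rate = ((127s − 20)r0 + 127(1 − s)r1)/107.

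- s = 0.5, r0 = 15%, r1 = 55%: (43.5×0.15 + 63.5×0.55)/107 = 38.7%. An adjustment with no effect shows 15 − 38.7 = −23.7 points; a true +15 shows 30 − 38.7 = −8.7.
- s = 0.3, r0 = 11.7%, r1 = 45%: (18.1×0.117 + 88.9×0.45)/107 = 39.4%. No effect shows −27.7 points; a true +15 shows −12.7.

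With a true +15, the first scenario's overall EBV rate rises to (44.45 + 3)/127 = 37.4%, slightly above the 35% anchor.

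**Opposing bias.** Adjustment follows the 45-day scan and may occur as late as Day 90. Adjusted participants have therefore remained in the study until then, while earlier deaths and exits fall in the comparator. This favours the adjusted group. The documents give nothing from which to size it.

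**Like-for-like comparison.** Among participants meeting both HRCT criteria, suppose half are adjusted (m per group), with response 20% if adjusted and 10% if not. The SE is √((0.20×0.80 + 0.10×0.90)/m) = √(0.25/m), and the 95% half-width is 1.96 times that: 40 points for 12 eligible (m = 6), 33 for 18 (m = 9), 25 for 30 (m = 15). The expected difference equals the true benefit only if the investigator's choice among eligible participants is itself unconfounded.

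**The case against.** The strongest reply is that the SAP claims nothing causal here. Section III.E is conditional, section VI names no test, and the primary and secondary endpoints are analysed by ITT. That stands, and it sets the weight of the point: this is about interpreting a supportive table. It does not remove the point, because the SAP orders the contrast without saying what it can and cannot show.

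The size rests on assumed inputs, and Protocol 12.3 expects only a few misplaced valves. That also stands. However, f does not affect the expected sign in Illustration A. What matters is how strongly eligibility predicts non-response, and weak selection produces no reversal.

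Three stronger readings are tempting but not supported:

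- **Controls are in the comparator.** Section VI does not say EBV-treated, so a reader might infer this. Protocol 12.0 and the SAP's Study Design paragraph confine secondary procedures to EBV-treated participants, so the natural comparator is EBV-treated participants without one. The wording should say so, but no figure here depends on the other reading.
- **Poor volume reduction defines all three groups.** It defines eligibility for adjustment only. Removal and replacement have other triggers, and Protocol 15.3.1 notes that greater success may come with more pneumothorax, so harm and poor response are not the same thing.
- **The bias has a known direction.** Selection on poor response works against adjustment, but the need to stay in follow-up works for it.

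**Conclusion.** The point holds as a problem of confounding by indication in a supportive analysis. Under strong assumed selection, a true benefit of 10 to 15 points shows as about −9 to −18 points (−8.7, −12.7 and −17.5 in the three worked cases). When those selected would have responded nearly as often as the whole arm, the sign is right. These sizes rest on assumed values of f, p0, b, s, r0 and r1; only the 35% anchor comes from the plan, and the 14.5% base value of f is borrowed from a different event. They also leave out the opposing follow-up bias, so the net direction is not certain.

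A reader might infer that the trial's main conclusions are at risk. They are not: the ITT primary and secondary results and their type I error do not use this contrast. Nor does the point bear on which clinical criteria for secondary procedures are right. The change is worth making because it is cheap and prevents a misleading table.

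**What to change.** In revised SAP sections III.E and VI:

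1. Limit these analyses to EBV-treated participants.
2. Report removal, replacement and adjustment separately, each with its reasons. Keep removal and replacement descriptive and do not contrast them with the rest.
3. For adjustment, replace the all-others comparator with non-adjusted EBV participants who also met both 45-day HRCT criteria. Matching on volume reduction alone is not enough, because it admits participants with complete occlusion and little reduction.
4. Apply the same landmark, alive and in follow-up at Day 90, to both groups. Imposing it on the comparator alone would count early deaths against adjustment only.
5. Label the result descriptive.
6. Accompany any within-person change from the 45-day CT and FEV1 with a note on regression to the mean, since these participants are selected for a poor 45-day scan.

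The cost is SAP wording. The 45-day HRCT and spirometry are already scheduled for EBV-treated participants, the core laboratory already assesses both criteria, and Protocol 13.11 already plans a 3-month scan after adjustment. The downside is precision: a 95% half-width of roughly 25 to 40 points for 30 down to 12 eligible participants. The landmark also drops anyone who dies or leaves before Day 90, so those participants should be counted alongside.

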13.2.3 Baseline/Transitional Dyspnea Index (BDI/TDI)

The BDI/TDI is used to quantify dyspnea and its validity has been reported [33]. The BDI will be collected at the baseline visit and the TDI should be collected at the 3-month, 6-month, 9-month, and 1-year follow-up visits. The assessment measures three domains: 1) functional impairment, which determines the impact of breathlessness on the ability to carry out activities; 2) magnitude of task, which determines the type of task that causes breathlessness; and 3) magnitude of effort, which establishes the level of effort that results in breathlessness. The score ranges from -3 (major deterioration) to +3 (major improvement) for each domain. The sum of all domains is the total score. A change of at least 1 unit is thought to represent a clinically meaningful effect.

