Table 3. Secondary Effectiveness Endpoints

Variable	Unit	Values Statistically Assessed
Target Lobe Volume Reduction (TLVR)	milliliters	mean absolute change
TLVR	percent	mean percent change
SGRQ Global Score	Points	mean absolute change
SGRQ	percent	mean percent change
FEV ₁	Liters	mean absolute change
FEV ₁	percent	mean percent change
6-Minute Walk Distance	Meters	mean absolute change

6MWD	percent	mean percent change
------	---------	---------------------

C. Analysis of Additional Effectiveness Endpoints

a. Supporting Evidence for Effectiveness

The following additional effectiveness endpoints will be measured for both study arms. These are expected to provide supporting evidence of the effectiveness of EBV treatment. Results will be described with summary statistics. These endpoints will be described for each study arm separately and comparatively between arms by calculating mean change or difference in proportions, whichever is appropriate for the variable being analyzed. The definitions for these additional effectiveness endpoints are shown in Table 4.

Table 4. Additional Effectiveness Endpoints

Spirometry Measures		
FEV ₁	≥12% improved	Percentage of participants
Forced Vital Capacity (FVC)	liters	mean absolute and percent change
FEV ₁ /FVC	ratio	mean absolute change
DL _{co}	percentage	mean absolute and percent change
Body Plethysmography Measures		
Residual Volume (RV)	liters	mean absolute and percent change
Inspiratory Capacity (IC)	liters	mean absolute and percent change
Functional Residual Capacity (FRC)		mean absolute and percent change
Total Lung Capacity (TLC)	liters	mean absolute and percent change
RV/TLC	ratio	mean absolute change
IC/TLC	ratio	mean absolute change
Patient-Reported Health Status Measures		
SGRQ Global Score	≥4 points improved	percentage of participants
	≥8 points improved	percentage of participants
SGRQ Domain Scores		
‘Symptoms’	points	mean absolute change
‘Activity’	points	mean absolute change
‘Impacts Daily Life’	points	mean absolute change
mMRC Score	semi-quantitative scale score	mean absolute change
COPD Assessment Test (CAT)	points	mean absolute change
Transitional Dyspnea Index (TDI)	points	mean absolute change
	≤1 point improved	percent of participants
Short Form (SF)-36 Health Survey	points	mean absolute change
EQ-5D Health Survey	points	mean absolute change
Other Measures		
BODE Index	semi-quantitative scale score	mean absolute change

	≤1, 0, ≥1 change	percentage of participants

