	scale score	!		
COPD Assessment Test (CAT)	points		mean absolute change	
Transitional Dyspnea Index (TDI)	points		mean absolute change	
	<1 point im	proved	percent of participants	
Short Form (SF)-36 Health Survey	points		mean absolute change	
EQ-5D Health Survey	points		mean absolute change	
Other Measures				
Target Lobe Volume Reduction (TLVR)	milliliters		mean absolute change	

Table 4. Additional Effectiveness Endpoints

Other Measures		
Target Lobe Volume Reduction	milliliters	mean absolute change
(TLVR)		_
TLVR	percent	mean percent change
BODE Index	semi-quantitative scale	mean absolute change
	score	
	< 1, 0, > 1 change	percentage of participants
6MWD	percent	mean percent change
6MWD	Meters	mean absolute change at
		6 months
6MWD	25 meters improved	percentage of participants
6MWD	>54 meters improved	percentage of participants
6MWD – subjects stratified by	meters	mean absolute change
distance walked at baseline		
Borg Scale Dyspnea Score:	semi-quantitative scale	mean absolute change
Before 6MWD test	score	

Borg Scale Dyspnea Score:	semi-quantitative scale	mean absolute change
After 6MWD test	score	

b. Informational Purposes:

The following additional effectiveness endpoints will be measured in both treatment groups for informational purposes. Results will be described with summary statistics (see Table 5). These endpoints will be described for each treatment group separately and comparatively between groups by calculating mean change or difference in proportions, whichever is appropriate for the variable being analyzed.

Table 5. Informational Variables

Variable	Unit	Values Statistically Assessed
Maintenance Medications		
Bronchodilators	change in medication regimen	percentage of participants
Corticosteroids	change in medication regimen	percentage of participants
Antibiotics	change in medication regimen	percentage of participants
Anti-Inflammatories	change in medication regimen	percentage of participants
Pulmonary Rehabilitation	reported adherence to	percentage of participants
Compliance Diary	program	
Adherence to program	number of sessions / week	mean absolute number
Intensity of program	length of reported sessions	mean absolute number
EXACT-PRO Diary Entries	points	mean absolute number
Health Utilization	frequency of use	percentage of participants
Measures		
Lung Radiographic		
Features		
TLVR	volumetric change	mean percentage change
valve occlusion	qualitative assessment	percentage of participants

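### The TDI responder row in SAP Table 4 has its inequality the wrong way round against the protocol's own threshold, and the BODE change classes in the same table overlap

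*Protocol*

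**What the plan says.** **TDI scale and threshold.** Protocol Section 13.2.3 describes three domains: "The score ranges from -3 (major deterioration) to +3 (major improvement) for each domain". It adds: "The sum of all domains is the total score". A higher total is therefore better. The same section gives the threshold: "A change of at least 1 unit is thought to represent a clinically meaningful effect".

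**TDI responder row.** Protocol Appendix 19, Section IV.C, Table 4 has two TDI rows. One is a mean absolute change in points. The other is a percentage of participants, defined as "≤1 point improved". The revised SAP of 26 October 2017, which supersedes Appendix 19, keeps the row in its own Table 4. Its text reads "<1 point im proved", where the underline beneath the sign (lost in plain text) makes it ≤. Neither document gives any other TDI responder rule.

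**Neighbouring rows.** In Appendix 19 Table 4 every other one-directional responder row uses ≥: FEV1 at 12%, SGRQ at 4 and 8 points (for example "≥4 points improved"), and 6MWD at 25 and 54 metres.

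**BODE row.** Table 4 in both documents reports percentages of participants in three change classes: ≤1, 0 and ≥1. In Section 13.12, more BODE points mean a worse state.

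**Role.** Of the Table 4 endpoints, Section IV.C says: "These are expected to provide supporting evidence of the effectiveness of EBV treatment". On the analysis it says: "Results will be described with summary statistics". The summary includes between-arm differences in mean change or in proportions.

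**The concern.** Section IV.C says that Table 4 holds the definitions of these endpoints, so a programmer would code the responder from that cell. The cell points the opposite way from Section 13.2.3. The change history records an update to Section IV(C), yet this row came through uncorrected in the operative text.

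At stake is a patient-reported dyspnoea result offered as support for effectiveness in a study meant for a premarket application. Coded as written, it cannot show the proportion with a clinically meaningful change, and on one reading it points the wrong way. Putting it right silently once results are known would be an undocumented change to a responder definition. The BODE row has a related fault: its percentages would not separate improved from unchanged participants.

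**Working it through.** The documents give no rate, power or sample size for the TDI responder, so there is no stated figure to reproduce.

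**Step 1. Which TDI totals each rule admits.** With three domains from -3 to +3, the total runs from 3 × (-3) = -9 to 3 × (+3) = +9. In whole points (an assumption) that is 19 values.

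| Rule | Totals admitted | Count |
|---|---|---|
| Section 13.2.3, taken as improvement: total ≥ +1 | +1 to +9 | 9 |
| Table 4 read as score ≤ 1 | -9 to +1 | 9 worsened + 1 unchanged + 1 = 11 |
| Table 4 read as improved by more than 0 and at most 1 | +1 | 1 |

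Both readings of Table 4 exclude the eight totals from +2 to +9. The only total that satisfies both Table 4 and Section 13.2.3 is +1.

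**Step 2. Scale direction does not explain the sign.** SGRQ falls as patients improve (Section 13.2.1), yet its row is still written with ≥ points improved. The word improved already carries the direction, so a TDI row in the same style would also take ≥.

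**Step 3. Effect on the arm difference (illustration only).** The documents give no TDI means or SDs. Assume a normal score rounded to whole points, with (EBV, control) means of (1, -0.5), (0.5, -0.5) or (0.5, 0) and SD 2.5, 3 or 3.5. With Φ the standard normal distribution function:

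- share ≤ 1 = Φ((1.5 - mean)/SD)
- share ≥ 1 = 1 - Φ((0.5 - mean)/SD)
- share at exactly +1 = Φ((1.5 - mean)/SD) - Φ((0.5 - mean)/SD)

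Worked case, SD 3, means 1 and -0.5:

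- ≤ 1: EBV Φ(0.167) = 56.6%; control Φ(0.667) = 74.8%; difference -18.1 points (from unrounded shares).
- ≥ 1: EBV 1 - Φ(-0.167) = 56.6%; control 1 - Φ(0.333) = 36.9%; difference +19.7 points.
- exactly +1: EBV 13.2%; control 11.7%; difference +1.5 points.

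Over all nine combinations, EBV minus control:

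| Rule | Smallest | Largest |
|---|---|---|
| score ≤ 1 | -5.3 | -20.9 |
| score ≥ 1 | +5.7 | +23.5 |
| exactly +1 | +0.3 | +2.6 |

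Each smallest value is at SD 3.5 with means (0.5, 0). Each largest is at SD 2.5 with means (1, -0.5).

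A second set of assumptions (control mean 0; EBV mean 0.5, 1 or 2; SD 2, 3 or 4; scores limited to -9 to +9) gives -4.5 to -37.2 points for ≤ 1, +4.8 to +37.2 for ≥ 1, and about 0 to 2 for exactly +1.

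**Step 4. BODE classes.** The index runs from 0 to 10, so a change runs from -10 to +10, which is 21 values. Class ≤1 holds 12 of them (-10 to +1), class 0 holds 1, and class ≥1 holds 10 (+1 to +10). The sum 12 + 1 + 10 = 23 exceeds 21 by 2 because a change of 0 and a change of +1 are each counted twice. The reported percentages therefore add to 100% plus the share at 0 plus the share at +1. Improvement is a negative change, and it has no class of its own: it is pooled with no change and with worsening by one point.

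**The case against.** The strongest reply is that this is a typographical slip which the documents themselves expose. Section 13.2.3 gives the threshold, the neighbouring rows show the intended direction, and listing 0 as its own BODE class makes a missing minus sign plain. That is probably how it arose. It does not make the cells harmless, because Table 4 is the stated definition and the slip survived a revision of that section.

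The second reply concerns consequence, and it stands in part. A reader might infer that the plan definitely counts worsened participants as responders and makes the arm that does worse look better. The text does not establish that. The cell says improved, and read as improved by up to 1 point it counts nobody who worsened and does not reverse the sign; it gives a near-zero difference. The reversal depends on reading the cell as a score of at most 1.

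The size is also limited evidence. Every scenario was set up with EBV better, so the direction follows from that assumption and is not a finding about the trial.

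Finally, the stakes are modest. The endpoints are additional and descriptive with no planned test, and the TDI mean-change row would sit beside the responder row with the correct sign. A reader might take the supporting-evidence label to mean that the effectiveness conclusion is at risk. It is not: study success rests on the FEV1 responder comparison alone, and the Hochberg procedure covers only absolute change in FEV1, 6MWD and SGRQ.

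**Conclusion.** The TDI responder row is wrong as written in the operative SAP. It contradicts the protocol's threshold, and on either reading it excludes all improvements of 2 points or more, so it cannot serve as a responder definition. Only the score reading adds unchanged and worsened participants and reverses the comparison: under the first set of assumptions control leads by about 5 to 21 points, where a cut-off of at least +1 has EBV leading by about 6 to 24. The improved-by-up-to-1 reading gives about 0.3 to 2.6 points, which is uninformative. These sizes rest on assumed means and SDs and on whole-point scores.

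The BODE classes overlap at 0 and +1 and do not isolate improvement. This is a separate and smaller fault.

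The primary test, alpha, power, study success, the Hochberg family and the TDI mean-change row are unaffected. The crossover comparison in Table 7 is also unaffected, as it includes neither TDI nor BODE.

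**What to change.** In Table 4 of the revised SAP:

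- TDI responder row: ≥1 point improved (TDI total score ≥ +1), to match Protocol Section 13.2.3.
- BODE row: ≤ -1 (improved), 0 (unchanged), ≥ +1 (worsened).

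Record both in the SAP change history as corrections. The cost is two table cells and two log entries. No new data are needed, and nothing changes in sample size, alpha or the confirmatory analyses.
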